This is an adaptive randomized phase II trial for low-risk MDS patients. Regarding the patients transfusion status, patients can be categorized as transfusion dependent and transfusion independent patients. It is expected that there will be half of the transfusion-dependent patients and half of transfusion-independent patients. For transfusion dependent patients, the goal is to compare three treatment arms: 1) DAC, 2) AZA3 (treatment of 3 days), and 3) AZA5 (treatment of 5 days). For transfusion independent patients, the goal is to compare four treatment arms: 1) best supportive care (BSC) 2) DAC, 3) AZA3 (treatment of 3 days), and 4) AZA5 (treatment of 5 days). The primary outcome is event free survival (EFS) defined as the time from beginning of treatment till an event occurs or last follow-up. For transfusion independent patients, the events includes lack of response, requirement of blood transfusion, progression to advanced stages of disease, transformation into AML, discontinuation of therapy due to side effects, and death. The patients who change from transfusion independence to transfusion dependence under BSC will be enrolled in transfusion-dependent group and adaptively assign to the three treatment arms, that is, DAC, AZA3, or AZA5. For transfusion dependent patients, the events includes lack of response, progression to advanced stages of disease, transformation into AML, discontinuation of therapy due to side effects, and death.

Study design

The maximum number of patients accrued will be 240. There will be two parallel adaptive randomization trials for transfusion dependent (N=120) and transfusion independent (N=120) patients respectively. Since we are expecting patients under BSC

will eventually become the transfusion dependent, it is assumed that initially there will be 120 patients under transfusion-dependent group, and the total number increases to about 150 after enrolling the approximate 30 patients under BSC.

Part I Transfusion dependent patients (N=150)

Design

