Patients will be randomized using a Bayesian adaptive algorithm. Patients will be randomized fairly among the three arms at the start of the trial (for the first 30 patients), that is, 10 patients per arm. Thereafter, as the trial progresses and data accrue, the randomization will become unbalanced in favor of the treatment that, on average, has better results in terms of event free survival. Therefore, each successive patient is more likely to receive the treatment with better results, on average. A minimum of 30 and a maximum of 150 patients will be accrued. There will be 12 months follow up after the last patient is accrued with an anticipated accrual rate of 5 patients per month.

Denote the event free survival for the patients in the three arms (DAC; AZA3; AZA5) as T_i for $i=1,2,3$. Assume the T_i is independent exponential with median μ_i . And each μ_i independently follows an inverse gamma distribution with parameter $\alpha=2.05$, $\beta=7.34$. The parameters were chosen to set the mean of the prior equal to 7 (the historical median EFS in months) and a variance of 1000. For each patient, the randomization probability for treatment arm i will be based on the posterior probability that it has the largest median EFS. For example, for arm 1, the posterior probability is $\pi_1=\Pr(\mu_1 > \mu_i)$ for $i=2,3$. In order to avoid aggressively favoring one arm too early in a large trial, instead of

assigning patients with posterior probability, we use its square root transformation as in the following formula to assign patients:

$$Aa = \frac{\sqrt{\pi_1}}{\sqrt{\pi_1} + \sqrt{\pi_2} + \sqrt{\pi_3}}, \text{ where } Aa \text{ is the probability of assigning patients to arm 1, } \pi_1 \text{ is}$$

the posterior probability that arm 1 is superior, etc.

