If at any point during the trial $Pr(\mu_i > \max\{u_j, \text{ for all } j \neq i\} | \text{data}) > 0.975$, the trial will be terminated and treatment i will be selected as superior. If at any point during the trial $Pr(\mu_i > \max\{u_j, \text{ for all } j \neq i\} | \text{data}) < 0.025$, then accrual to the arm i will be suspended, and will be reopen if in the future, the changes in other arms make this probability $Pr(\mu_i > \max\{u_j, \text{ for all } j \neq i\} | \text{data}) \geq 0.025$. If the maximum accrual is reached and $Pr(\mu_i > \max\{u_j, \text{ for all } j \neq i\} | \text{data}) > 0.8 (< 0.2)$, treatment i will be selected as superior (inferior). A treatment arm will be dropped at any point during the trial if $Pr(\mu_i > 7 | \text{data}) < 0.1$, for $i=1,2,3$. Table 3 given below summarizes operating characteristics of the design. The historical median EFS is assumed to be 7 months with the accrual rate of 5 patients per month. The trial will be stopped early and a treatment selected as being “better” if the probability that one treatment’s median EFS is larger than the other’s EFS exceeds 0.975. If the trial does not stop early and the maximum 150 patients are accrued, a treatment is selected as being “better” if the probability that one treatment’s median EFS is larger than the other’s EFS exceeds 0.8. A treatment arm will be dropped at any point during the trial if the probability that the treatment’s median EFS is larger than 7 months is less than 0.1. The “# of patients treated” row is

the average number of patients treated on a given arm under the given scenario.

When the medians all equal to 7 months (scenario 1), the probability of selecting one of the three arms (i.e., a false positive result) is at most 9.8%. The probability of selecting the best treatment (i.e., a true positive result) for scenario 2, when the medians EFS are 7, 7, and 12 months for the arms, respectively, are 0.7%, 0.7%, and 88%.

Table 3: simulation results (simulation=5000) for transfusion dependent patients with the minimum randomization probability set as 0.1 and tuning parameter as 0.5

		treatment		
		DAC	AZA3	AZA5
1	True Median EFS	7	7	7
	# of patients treated	40.1	40.6	40.5
	Pr(selected)	0.086	0.095	0.098
	Pr(selected early)	0.003	0.006	0.005
	Pr (stopped early)	0.321	0.317	0.316
2	True Median EFS	7	7	12
	# of patients treated	28.5	28.6	54.2
	Pr(selected)	0.007	0.007	0.88
	Pr(selected early)	0.0002	0.001	0.188

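### The stopping and selection rule is given once as larger than all other arms and again as a looser two-arm comparison; the wording needs aligning with the formula

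*Combined protocol and SAP*

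**What the plan says.** Section XII (Statistical Considerations) runs two parallel trials. In Part I, "For transfusion dependent patients, the goal is to compare three treatment arms: 1) DAC, 2) AZA3 (treatment of 3 days), and 3) AZA5" is the stated aim. In Part II, "For transfusion independent patients, the goal is to compare four treatment arms", the fourth being BSC.

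Each Design section states the selection rule first as a formula. Arm i is selected early if the posterior probability that its median exceeds the maximum of all other medians is above 0.975. At maximum accrual the limit is "Pr(\mu_i > \max\{u_j, \text{ for all } j \neq i\} | \text{data}) > 0.8 (< 0.2"), where the bracketed limit is for naming an arm inferior.

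Each section then introduces its table of operating characteristics and states the rule again in words. The trial stops early, or a treatment is called better at full accrual, "if the probability that one treatment’s median EFS is larger than the other’s EFS exceeds 0.8"; the early version is the same sentence with 0.975. The wording is the same for three arms and for four. Neither part says which statement governs, or that the second only paraphrases the first.

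**The concern.** The prose compares one treatment with a single other one. That is complete for two arms, but there are six ordered pairs among three arms and twelve among four, and the prose does not say which pair counts. Taken literally, any one pair over the limit is enough. An arm that beats only the worst arm would then qualify, and two arms could qualify together. Under the formula two arms cannot both qualify, because the probabilities of being best sum to 1 and only one can exceed 0.8.

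This rule decides whether a part stops early and what its primary conclusion is. Someone applying the prose could stop a part, or name a winner, on evidence that the formula treats as inconclusive. The error rates printed beside the prose would not apply to that decision.

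**Working it through.** **Inputs (section XII, Design of each part).**
- Part I: 3 arms, equal randomization "for the first 30 patients), that is, 10 patients per arm". Between 30 and 150 patients in total, 5 per month, 12 months of follow-up. Prior inverse gamma (2.05, 7.34) on each median; historical median 7 months.
- Part II: 4 arms, first 40 patients equally randomized, maximum 120, 4 per month, 12 months of follow-up. Prior inverse gamma (2.14, 13.73); historical median 12 months.
- Both: exponential EFS, square-root allocation with minimum probability 0.1, and an arm dropped if Pr(median > historical) < 0.1.

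**Step 1: which rule produced the tables.** Each part was simulated patient by patient. The posterior for a median is inverse gamma (α + events, β + ln 2 × exposure). Looks were taken at each arrival after the run-in and 12 months after the last patient. Runs had 1,000–2,500 trials. Under the formula rule:

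| Quantity | Plan | Simulated |
|---|---|---|
| Part I scenario 1, selected per arm | 0.086–0.098 | 0.072–0.078 |
| Part I scenario 2, best arm selected | 0.88 | 0.851 |
| Part I scenario 2, best arm selected early | 0.188 | 0.168 |
| Part I scenario 3, patients per arm | 10.5 | 10.5 |
| Part I scenario 5, two better arms | 0.242 / 0.235 | 0.22 / 0.248 |
| Part II scenario 1, selected per arm | 0.029–0.037 | 0.022–0.034 |
| Part II scenario 5, best arm selected | 0.797 | 0.766–0.775 |

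The match is close but not exact. The plan does not document how its software handles dropped arms or times its looks.

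Selections are mutually exclusive under the formula, so the plan's any-arm null rates are sums over arms:
- Part I: 0.086 + 0.095 + 0.098 = 0.279, of which early 0.003 + 0.006 + 0.005 = 0.014.
- Part II: 0.037 + 0.036 + 0.034 + 0.029 = 0.136, of which early 3 × 0.001 + 0.0004 = 0.0034.

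The simulated formula rule gives about 22% and 11–12%.

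**Step 2: one look, equal information per arm.** Posterior differences are approximately normal, so some pair exceeds limit p when the range of k standard normals exceeds z(p) × √2.
- p = 0.8: 0.8416 × 1.4142 = 1.190. P(range > 1.190) = 0.677 for k = 3 and 0.835 for k = 4.
- p = 0.975: 1.960 × 1.4142 = 2.772. P(range > 2.772) = 0.12 for k = 3 and 0.20 for k = 4.
- Two or more arms qualify together at 0.8 when the second-best arm beats the worst by more than 1.190: probability 0.26 for k = 3 and 0.52 for k = 4.

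**Step 3: full design, equal medians, only the selection rule changed.** Share of trials naming at least one better arm:

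| Rule | Part I | Part II |
|---|---|---|
| Formula, larger than all others | about 22% | 11–12% |
| Any pair, open arms only | 22–30% | 39–46% |
| Any pair, dropped arms kept as comparators | 73–81% | 88–91% |
| Any pair at the final look only, early look by formula | 69% | 85% |

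Early stopping for superiority under the any-pair reading is about 12–13% in both parts with open arms only. With dropped arms kept it is roughly 33–51% in Part I and 48–61% in Part II. The table values from Step 1 are 1.4% and 0.3%.

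**The case against.** The strongest reply is that the plan already fixes the rule. The formula is explicit in both parts, and the allocation text uses the same idea, the probability of having the largest median. The disputed sentences sit next to the table introduction and read like a legend; the historical drop rule is restated there in the same way. The singular possessive may be a slip for the plural. The tables agree approximately with the formula, and allocation runs through the biostatistics department's trial website. All of this stands. It means that the intended rule is not in doubt and that the stated operating characteristics belong to it.

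The size also depends heavily on the reading. The high figures need two assumptions: that any pair counts, and that an arm already dropped remains a comparator. With open arms only, the Part I range starts at the formula rule's own level, so the excess there may be small or nil. In Part II it is still roughly three to four times the formula rule.

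The reply does not remove the conflict. The prose is a complete rule with its own limits, it governs termination and the primary conclusion, and nothing marks it as subordinate.

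A reader might go further and infer that the design has a false-positive rate of 70–90%, or that Tables 3 and 6 are wrong. The documents support neither. Those rates arise only if the prose is applied instead of the formula, and the tables' low null and early-selection rates are what the formula produces. The inexact reproduction reflects undocumented software conventions and is not evidence against the tables.

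**Conclusion.** The concern holds as an inconsistency between two statements of the primary decision rule. It is not a fault in the simulated design. The formula is the intended rule; the prose is looser, and the 9.8%, 3.7%, 88% and 79.7% do not describe it.

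With equal medians, following the prose would name a better arm in anywhere from about 22% to 81% of Part I trials and 39% to 91% of Part II trials, depending mainly on whether dropped arms still count. The simulations assume exponential EFS, the plan's priors and accrual rates, a look at every arrival after the run-in, and that any single pair suffices. The variants differ in how they treat dropped and suspended arms, which the plan leaves open. The conflict itself rests on the text alone and needs none of these assumptions.

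**What to change.** In the Design text of both Part I and Part II, replace the two prose sentences (0.975 and 0.8) with: *a treatment is selected as better only if the posterior probability that its median EFS is larger than the median EFS of every other arm exceeds 0.975 (early) or 0.8 (at maximum accrual)*. Alternatively, delete them and let the formula stand alone.

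The historical arm-drop rule, the provisions at 0.025, the inferiority limit of 0.2 and the toxicity boundaries should stay as they are. The new text should not claim to be the only rule for stopping and selection, because that would contradict each of these.

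The cost is a wording change in each part. It needs no extra patients or data, and no new simulation, since Tables 3 and 6 already reflect the formula.

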Table 5: Operating characteristics of safety monitoring

True Toxicity Rate	Prob (stop the trial early)
0.15	0.04
0.2	0.25
0.25	0.68
0.3	0.94

Part II: Transfusion independent patients (N=120)

Design

Patients will be randomized using a Bayesian adaptive algorithm. Patients will be randomized fairly among the four arms at the start of the trial (for the first 40 patients), that is, 10 patients per arm. Thereafter, as the trial progresses and data accrue, the randomization will become unbalanced in favor of the treatment that, on average, has better results in terms of event free survival. Therefore, each successive patient is more likely to receive the treatment with better results, on average. A minimum of 40 and a maximum of 120 patients will be accrued. There will be 12 months follow up after the last patient is accrued with an anticipated accrual rate of 4 patients per month.

Denote the event free survival for the patients in the four arms (BSC; DAC; AZA3; AZA5) as T_i for $i=1,2,3,4$. Assume the T_i is independent exponential with median μ_i . And each μ_i independently follows an inverse gamma distribution with parameter $\alpha=2.14$, $\beta=13.73$. The parameters were chosen to set the mean of the prior equal to 12 (the historical median EFS in months) and a variance of 1000. For each patient, the randomization probability for treatment arm i will be based on the posterior probability that it has the largest median EFS. For example, for arm 1, the posterior probability is $\pi_1=\Pr(\mu_1 > \mu_i)$ for $i=2,3,4$. In order to avoid favoring one arm earlier in a large trial, instead of assigning patients with posterior probability, we use the following formula to assign patients:

$Aa = \frac{\sqrt{\pi_1}}{\sqrt{\pi_1} + \sqrt{\pi_2} + \sqrt{\pi_3} + \sqrt{\pi_4}}$, where Aa is the probability of assigning patients to arm 1, π_1 is the posterior probability that arm 1 is superior, etc.

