If at any point during the trial $\Pr(\mu_i > \max(u_j \text{ for all } j \neq i) | \text{data}) > 0.975$ (< 0.025), the trial will be terminated and treatment i will be selected as superior (inferior). If the maximum accrual is reached and $\Pr(\mu_i > \max\{u_j \text{ for all } j \neq i\} | \text{data}) > 0.8$ (< 0.2), treatment i will be selected as superior (inferior). A treatment arm will be dropped at any point during the trial if $\Pr(\mu_i > 12 | \text{data}) < 0.1$, for $i=1,2,3,4$. Table 6 given below summarizes operating characteristics of the design. The historical median EFS is 12 months. The tables below assume an accrual rate of 4 patients per month. The trial will be stopped early and a treatment selected as being “better” if the probability that one treatment’s median EFS is larger than the other’s EFS exceeds 0.975. If the trial does not stop early and the maximum 120 patients are accrued, a treatment is selected as being “better” if the probability that one treatment’s median EFS is larger than the other’s EFS exceeds 0.8. A treatment arm will be dropped at any point during the trial if the probability that the treatment’s median EFS is larger than 12 months is less than 0.1. The “# of patients treated” row is the average number of patients treated on a given arm under the given scenario. When the medians all equal to 12 months (scenario 1), the probability of selecting one of the three arms (i.e., a false positive result) is at most 3.7 %. The probability of selecting the best treatment (i.e., a true positive result) for scenario 5, when the medians TTP are 12, 12, and 24 months for the arms, respectively, are 0.1%, 0.04%, 0.2%, and 79.7%.

Table 6: simulation results (simulation=5000) for transfusion dependent patients with the minimum randomization probability set as 0.1 and tuning parameter as 0.5

			treatment		
		BSC	DAC	AZA3	AZA5
1	True Median EFS	12	12	12	12
	# of patients treated	29	28.9	28.8	28.6

	Pr(selected)	0.037	0.036	0.034	0.029
	Pr(selected early)	0.001	0.001	0.001	0.0004
	Pr (stopped early)	0.235	0.233	0.253	0.244
2	True Median EFS	7	7	7	7
	# of patients treated	14.2	14.3	14.3	14.4
	Pr(selected)	0.029	0.024	0.027	0.027
	Pr(selected early)	0.0002	0	0.0002	0.0002
	Pr (stopped early)	0.764	0.774	0.773	0.755
3	True Median EFS	7	12	15	20
	# of patients treated	13.2	24.2	32.3	42
	Pr(selected)	0	0.003	0.035	0.496
	Pr(selected early)	0	0.0004	0.003	0.036
	Pr (stopped early)	0.971	0.58	0.296	0.032
4	True Median EFS	12	12	12	20

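### The stated false-positive rates of 9.8% and 3.7% are single-arm maxima; Tables 3 and 6 give 27.9% (Part I) and 13.6% (Part II) for selecting any arm

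*Combined protocol and SAP*

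**What the plan says.** Section XII (Statistical Considerations, Study design) sets up two separate comparisons: "There will be two parallel adaptive randomization trials for transfusion dependent (N=120) and transfusion independent (N=120) patients respectively". Each has its own simulated operating characteristics.

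- **Part I, text before Table 3.** With all medians at the historical 7 months, "the probability of selecting one of the three arms (i.e., a false positive result) is at most 9.8" percent. Scenario 1 of Table 3 lists, for DAC, AZA3 and AZA5: "Pr(selected) 0.086 0.095 0.098".
- **Part II, text before Table 6.** With all medians at 12 months, "the probability of selecting one of the three arms (i.e., a false positive result) is at most 3.7" percent. Scenario 1 of Table 6 lists, for BSC, DAC, AZA3 and AZA5: "Pr(selected) 0.037 0.036 0.034 0.029". The sentence refers to three arms, but the Part II design has four: "Patients will be randomized fairly among the four arms at the start of the trial".

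In both Parts an arm is selected if its posterior probability of having the largest median EFS exceeds 0.975 during the trial, in which case "the trial will be terminated and treatment i will be selected as superior". Otherwise it is selected if that probability exceeds 0.8 once maximum accrual is reached. No probability of selecting any arm at all under equal medians is given anywhere.

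**The concern.** Both sentences equate the selection of an arm under equal medians with a false positive result and then put an upper bound on its probability. The bound is the largest entry for one arm. A trial with three or four equal arms has three or four ways to make a false selection, and the probability of the trial making one covers all of them.

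A reader is therefore told that the risk of wrongly naming a superior arm on the primary endpoint is below 10% in Part I and below 4% in Part II. These two sentences are the plan's only narrative statements of a false-positive rate for EFS, and the Analysis Plan names a logrank test without a significance level. Any later claim that one regimen is superior will be read against these figures.

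**Working it through.** **Inputs.** Pr(selected) from scenario 1 of Table 3 (0.086, 0.095, 0.098) and of Table 6 (0.037, 0.036, 0.034, 0.029); the selection thresholds 0.975 and 0.8; 5000 simulated trials, as given in both table captions.

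**1. Reproduce the stated figures.**
- Part I: max(0.086, 0.095, 0.098) = 0.098, the AZA5 entry.
- Part II: max(0.037, 0.036, 0.034, 0.029) = 0.037, the BSC entry.

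Both match the text exactly, so the stated figures are per-arm maxima.

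**2. Can two arms be selected in one trial?** Let p_i be the posterior probability that arm i has the largest median. Across the arms compared, the p_i sum to 1. If p_i > 0.8, every other p_j is below 0.2, so no second arm can pass 0.8 or 0.975. Early selection also ends the trial. The selections are mutually exclusive, and the probability of selecting any arm is the plain sum of the entries. Without exclusivity, the largest entry would still be a lower bound on the any-arm probability, not an upper bound.

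**3. Is early selection already included in Pr(selected)?** In Table 3, scenario 6, AZA5 has Pr(selected) = 0.883 and Pr(selected early) = 0.357. Their sum is 1.240, which is above 1. Pr(selected) must therefore already contain early selections, and nothing is to be added.

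**4. Any-arm totals under equal medians at the historical value.**

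| | Sum | Total | Stated | Ratio |
|---|---|---|---|---|
| Part I | 0.086 + 0.095 + 0.098 | 0.279 | 0.098 | 2.85 |
| Part II, all arms | 0.037 + 0.036 + 0.034 + 0.029 | 0.136 | 0.037 | 3.68 |
| Part II, drug arms only | 0.036 + 0.034 + 0.029 | 0.099 | 0.037 | 2.68 |

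**5. Simulation error.** SE = sqrt(p(1 − p)/5000).
- Part I: sqrt(0.279 × 0.721/5000) = 0.0063.
- Part II: sqrt(0.136 × 0.864/5000) = 0.0048; drug arms only, sqrt(0.099 × 0.901/5000) = 0.0042.

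The gaps to the stated figures are 18.1, 9.9 and 6.2 percentage points, far beyond these errors.

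**6. Other equal-median scenarios, for information.** Table 3, scenario 3 (all 3 months): 0.046 + 0.043 + 0.045 = 0.134. Table 6, scenario 2 (all 7 months): 0.029 + 0.024 + 0.027 + 0.027 = 0.107.

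**7. Cross-check, not relied on.** A simulation of the design as written (exponential EFS, the stated priors, square-root allocation with minimum 0.1, the dropping rule, 12 months' follow-up; 1000 runs per Part) gave any-arm rates of 21.8% and 10.6%. No run selected two arms. The rates fall short of the table totals, and the software's internal settings are not documented. They are still well above 9.8% and 3.7%.

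**The case against.** The strongest reply is that the wording can be read arm by arm. The phrase at most suits a bound over several per-arm figures better than one overall probability, and the next sentence in each Part reports results for each arm separately. On that reading 9.8% and 3.7% are correct numbers. Every per-arm entry is also printed in the table that follows, so nothing is hidden. The plan sets no target error rate that 27.9% would breach, and a phase II selection design may accept such a rate.

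Much of this is true, but it does not rescue the sentences. They call the event the false positive result. Under equal medians that event is the selection of any arm, and its rate is not stated anywhere.

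Some narrower objections stand in part:

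- The two sentences concern scenario 1 only, so the totals of 13.4% and 10.7% in the other equal-median scenarios do not contradict them. The per-arm maxima there, 4.6% and 2.9%, lie below the quoted values.
- The drug-arms-only figure of 9.9% uses a definition that the plan does not use, since its 3.7% is the BSC entry. It is useful to report but is not the plan's own quantity.
- The count of three arms in Part II is an editorial slip.
- The totals are properties of the sponsor's tables. The cross-check did not reproduce them exactly, so they should be cited as coming from Tables 3 and 6.

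**Conclusion.** The concern holds. By the plan's own simulations, the probability of falsely selecting an arm when all medians equal the historical value is 27.9% in Part I and 13.6% in Part II (9.9% counting drug arms only), against stated bounds of 9.8% and 3.7%. The understatement is about 2.8-fold and 3.7-fold.

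The result rests on two assumptions: that the printed Pr(selected) entries are right, and that the software applied the rule as its formula is written, with one arm compared against the maximum of the others. It needs no re-simulation. No allocation, dropping or selection rule uses the two figures, so conduct of the trial is unaffected. The error lies in a stated design property.

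A secondary point does not carry the finding. At maximum accrual an arm whose probability of being best is below 0.2 is declared inferior, and no error rate is given for that rule. With four equal arms the average probability of being best is 1/4 = 0.25, close to that cut-off. No percentage is claimed here.

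**What to change.** - **Part I:** state that, with all medians at 7 months, the probability of selecting any arm is 27.9% (sum of the scenario 1 entries in Table 3), and label 9.8% as the largest per-arm value.
- **Part II:** state 13.6% for any arm with all medians at 12 months (9.9% for a drug arm), label 3.7% as the largest per-arm value, and change the count from three arms to four.
- **Secondary:** report the probability that the end-of-accrual inferior rule labels an arm inferior when all arms are equal, from the sponsor's own simulation, beside the superiority figures.

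The first two changes cost one sentence in each Part. The third needs one further output from the simulation, which Tables 3 and 6 do not currently show. No decision rule, sample size or existing table entry has to change. The price is that the stated error rates become less favourable.

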	# of patients treated	24	24.3	23.8	40.7
	Pr(selected)	0.003	0.004	0.006	0.572
	Pr(selected early)	0	0.0002	0.0002	0.027
	Pr (stopped early)	0.538	0.533	0.544	0.014
5	True Median EFS	12	12	12	24
	# of patients treated	22.3	22.3	22	42.5
	Pr(selected)	0.001	0.0004	0.002	0.797
	Pr(selected early)	0	0.0002	0	0.059
	Pr (stopped early)	0.713	0.719	0.721	0.006

The design software adaptive Randomization version 4.1.1. developed by the Department of Biostatistics at M. D. Anderson Cancer Center (MDACC) was used to generate the OC table.

Toxicity Monitoring

Evidence of Toxicity will be monitored closely for all patients except for the patients under the BSC. With 10 patients fairly randomized to each arm of the four arms, there will be at most 80 patients being adaptively assigned to any arm. Taking the initial 10 patients assigning to each arm, the maximum number of patient per treatment arm will be 90. For each treatment, treatment will be terminated if $\Pr(\theta_E > 0.2 | \text{data}) > 0.88$. where θ_E is the proportion of any grade 3 or greater treatment related non-hematologic toxicities attributed to study drug and is assumed to follow a non-informative prior of Beta (0.4, 1.6) That is, the trial will be terminated if at any time during the study, there is a more than 88% chance that the average rate of grade 3 or greater treatment related

non-hematologic toxicity is more than 20%. Patients will be monitored by a cohort size of 10 according to the following stopping boundaries for toxicity. The design software Multc Lean Desktop (version 2.1) developed by the Department of Biostatistics at M. D. Anderson Cancer Center (MDACC) was used to generate the futility/toxicity stopping boundaries and the OC table.

Table 7: stopping boundaries for toxicity

Number of patients evaluated	Stop the trial if there are this many treatment related toxicities
10	4-10
20	7-20
30	9-30
40	12-40
50	14-50
60	17-60
70	19-70
80	21-80

Table 8: Operating characteristics of safety monitoring

True Toxicity Rate	Prob (stop the trial early)
0.15	0.08
0.2	0.28
0.25	0.62
0.3	0.88

Analysis Plan

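### Part II as written ends the whole four-arm trial once any one arm looks inferior, a rule that cannot have produced Table 6 or its 79.7%

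*Combined protocol and SAP*

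**What the plan says.** Section XII, Part II, Design, monitors for each of the four arms (BSC, DAC, AZA3, AZA5) the posterior probability that it has the longest median EFS, called Pr(best) below. If this exceeds 0.975 or falls below 0.025 at any point, "the trial will be terminated and treatment i will be selected as superior (inferior". Both tails share that one consequence.

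Three other places bear on the lower limit:

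- **Part I, Design.** When Pr(best) falls below the same 0.025, "then accrual to the arm i will be suspended, and will be reopen if in the future" the other arms' results bring the probability back up.
- **Part II, restatement in words.** "The trial will be stopped early and a treatment selected as being" better once 0.975 is exceeded. Separately, an arm is dropped when the probability that its "median EFS is larger than 12 months is less than 0.1". No trial-level stop for inferiority is listed.
- **Table 6, scenario 5** (medians 12, 12, 12 and 24 months). The text gives the selection probabilities "for the arms, respectively, are 0.1%, 0.04%, 0.2%, and 79.7" percent. The table's row for arms stopped early reads "0.713 0.719 0.721 0.006".

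Without an early stop, selection needs Pr(best) above 0.8 at the maximum of 120 patients.

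**The concern.** In a four-arm trial, one arm with less than a 2.5% chance of being best is an ordinary finding and says little about which of the others is best. Followed literally, the sentence closes accrual to three possibly good arms. The 0.8 rule is never reached, so the adaptive design selects nothing. The Kaplan-Meier, log-rank and Cox analyses could still be done, but on roughly half the planned patients.

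This is the stopping rule for the primary endpoint. If Table 6 was produced under a different rule, the stated 79.7% describes a trial other than the one the protocol tells the monitoring board to run.

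**Working it through.** **1. Table 6 alone, scenario 5.** AZA5 is selected in 0.797 of runs, 0.059 of them early, so 0.797 − 0.059 = 0.738 are selections at the end. AZA3 is stopped early in 0.721. These two events overlap in at least 0.738 + 0.721 − 1 = 0.459 of runs. In at least 45.9% of runs, then, an arm was stopped and the trial still ran on to select AZA5.

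**2. Could those closures all come from the 12-month futility drop?** That rule uses only the arm's own data, so its closure rate for an arm with a true median of 12 months should not depend much on the fourth arm. In Table 6 it rises steeply as AZA5 improves:

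| Scenario | AZA5 median (months) | 12-month comparators stopped early |
|---|---|---|
| 1 | 12 | 23–25% |
| 4 | 20 | 53–54% |
| 5 | 24 | 71–72% |

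Early selection of AZA5 (2.7% and 5.9% in scenarios 4 and 5) is too rare to explain the rise. In simulation, futility alone closes a 12-month arm in 34–38% of runs in scenario 4 and 33–37% in scenario 5. Adding suspension at 0.025 gives 59–60% in scenario 5 with looks during accrual, or 69–71% if looks continue in follow-up. A comparative rule appears to close single arms without ending the trial.

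**3. Simulation inputs (Part II, Design, and Table 6 title).** Exponential EFS; inverse gamma (2.14, 13.73) prior on each median; 4 patients per month; 10 per arm equally, then square-root allocation with floor 0.1; futility drop if Pr(median > 12) < 0.1; selection at Pr(best) > 0.975 early, or > 0.8 after 12 months of follow-up. The posterior for a median is inverse gamma (2.14 + events, 13.73 + ln 2 × exposure). The prior mean is 13.73/1.14 = 12.04 and its variance 13.73²/(1.14² × 0.14) = 1036, in line with the stated 12 and 1000.

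**4. Main results (5,000 replicates per scenario).** The main reading has looks after patient 40, tests only open arms for inferiority, and keeps dropped arms in the comparison. Ranges cover 48 readings in scenario 5 and 12 in scenarios 3 and 4, varying look schedule, order of checks and handling of dropped arms.

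| Scenario (medians) | Table 6: AZA5 selected; total N | Arm suspended, can reopen | Whole trial ends, as written |
|---|---|---|---|
| 5 (12/12/12/24) | 79.7%; 22.3 + 22.3 + 22 + 42.5 = 109.1 | 79.8%; N 112.5 | 12.7% (0.1–29%) |
| 4 (12/12/12/20) | 57.2%; 24 + 24.3 + 23.8 + 40.7 = 112.8 | 56.0% | 13.3% (1–29%) |
| 3 (7/12/15/20) | 49.6%; 13.2 + 24.2 + 32.3 + 42 = 111.7 | 49.8% | 15.7% (0–32%); N 85 (41–96) |

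Under suspension, scenario 5 ranges from 77% to 84% over 16 variants. As written, 62–80% of trials in scenarios 3 to 5 end for an inferior arm; in scenario 5 it is 80%, at a median of 61 patients. With four identical 12-month arms it is 38% (22–83%).

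**5. Separately coded simulation, scenario 5 (400 to 1,500 trials per run).** Suspension gives 79.9% with dropped arms kept in the comparison and 83.1% with them excluded. As written it gives 10.5% and 19.9%, with mean N 74.7 and 76.8.

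**6. Most generous reading.** Suppose a leading arm with Pr(best) > 0.8 could still be picked when the trial ends for inferiority, which the text does not provide for. Selection is then 10–52% at the stop, or 31–66% after 12 more months of follow-up, still short of 79.7%.

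**The case against.** The strongest reply accepts that the literal rule cannot give 79.7% but disputes what Table 6 does show.

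- **Selection rates do not identify the rule.** With no 0.025 rule at all, scenario 5 selection is 81.1% with mean N 110.8, close to suspension. This stands. The rising stopped-early row favours a comparative arm-level rule, but only the software settings can settle it.
- **Table 6 does not fit suspension fully either.** If trials end before 120 only by early selection or closure of all arms, scenario 5 loses at most (120 − 40) × (0.059 + 0.0002 + 0.006) = 5.2 patients, so mean N should be at least 114.8, against 109.1. Some further ending may be built into the software. In one short run, stopping accrual once a single arm remained cut early selection from 30% to 9% (Table 6: 5.9%). This stands as a reason to check the settings; it does not rescue the written rule, whose mean N is about 75 to 77.
- **The simulation misses some rows.** Early selection in scenario 5 is 25–27% against 5.9%, and stopped early under the null is about 40–43% against 23–25%. The separate simulation counts 44–48% of weaker arms stopped under suspension in scenario 5. With all medians at 7 months, a check run stops 98–99% of arms at N about 71, against 75.5–77.4% and 57.2. Look timing and the definition of stopped early are not given. The null figure of 38% is therefore the least secure result.
- **The two parts are separate trials and may have different rules, and the restatement conflicts only by omission.** Both are fair. The conflict with Table 6 does not depend on either.

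**Conclusion.** The concern holds. The written Part II rule conflicts with Table 6, differs from Part I, and has no counterpart in Part II's own restatement. In scenario 5 the rule as written selects the best arm in about 13% of trials, and in no more than 29% under any literal reading, against the stated 79.7%. Scenarios 3 and 4 show gaps of the same kind.

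The result rests on exponential EFS, the stated prior, accrual and thresholds, and an assumed look schedule. The size of the gap is robust to that schedule; the exact percentages are not. That Table 6 used arm-level handling is the best-supported reading, but it is an inference until the settings are seen.

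**What to change.** 1. Check the settings behind Table 6: which consequence followed Pr(best) < 0.025, when looks took place, and whether anything else could end the trial.
2. Reconcile the Part II sentence with Part I and Table 6: keep whole-trial termination only for Pr(best) > 0.975, and make < 0.025 a suspension of accrual to that arm with reopening, as in Part I.
3. State whether dropped or suspended arms stay in the Pr(best) comparison.
4. If whole-trial termination for one inferior arm is truly intended, say so, re-run Table 6 under it and replace the 79.7%.

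The cost is one sentence and a check of settings. A re-run is needed only if the settings differ from the corrected text. No patients are added to the planned 120.
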